## **6.1 Dosage:**

Mylan will supply Imatinib as 100 mg tablets packaged in bottles for an exposure period of up to 6 months or so long as the patient remains on study. The starting dose for subjects will be 340 mg/m^2 with a maximum dose of 600 mg daily. Tablets can be broken in half, and therefore, drug doses will be rounded to nearest 50 mg according to the dosing table in the Appendix A. Dosing should be based on the body surface area (BSA) obtained at each clinic appointment.

The prescribed dose should be administered at the same time each morning, orally, with a meal and a large glass of water. Patients should keep normal eating habits, however a low-fat (i.e. continental) breakfast is recommended and avoiding xanthine (e.g. caffeine) or grapefruit containing food or beverages. If vomiting occurs > 15 minutes after administration of the dose, no additional trial medication should be taken that day in an effort to replace the material that has been vomited.

In the absence of dose limiting toxicity (DLT), patients may receive a total of 6 months of therapy. Continuing treatment beyond this period will be at the discretion of the investigator and may become the financial responsibility of the patient if no alternative method of obtaining or paying for the drug can be identified at that time. Medication labels will comply with the legal requirements of the US and will be printed in English. The storage conditions for Imatinib will be described on the medication label. Bottles must be stored in a safe, secure location.

See Section 8 and 9 for dose-limiting toxicities and dose reductions/modifications. If the toxicity resolves to meet study parameters within 14 days of drug discontinuation, the patient may resume treatment with the dose reduced by from 340 mg/m^2 to 260 mg/m^2. Treatment should resume 14 days from drug discontinuation even if toxicity has resolved before 14 days in order to allow for a full 2-week rest period before resuming drug. Subjects who fail to recover to a <= grade 2 or baseline within 14 days of AE onset will permanently discontinue study drug. This does not include the following AEs: nausea and fatigue (does not require dose reduction or discontinuation). Upon restarting drug, the dose will be reduced to 260 mg/m^2 (see table in Appendix A) and not re-escalated in subsequent cycles. A maximum of 2 dose reductions (340 mg/m^2 to 260 mg/m^2 to 200 mg/m^2) will be allowed before permanent discontinuation of study drug.

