##### **1. Non-hematologic dose-limiting toxicity**

- Any Grade 4 non-hematologic toxicity
- Any Grade 3 non-hematologic toxicity with the specific exception of:
  - Grade 3 ALT that return to levels that meet initial eligibility criteria within 7 days of study drug interruption and that do not recur upon rechallenge with study drug. Note: For the purposes of this trial the ULN for ALT is defined as 45 U/L.
  - Grade 3 AST
  - Grade 3 fever or infection <5 days duration
  - Grade 3 hypophosphatemia, hypokalemia, hypocalcemia or hypomagnesemia responsive to oral supplementation within 14 days of initiating supplementation
  - Asymptomatic Grade 3 elevations in amylase or lipase resolving to <Grade 1 within 7 days of study drug interruption and that do not recur upon re-challenge with study drug
- Grade 2 or greater left ventricular systolic dysfunction OR an absolute decrease in shortening fraction of 8 percentage points from baseline.
- Grade 2 allergic reactions that necessitate discontinuation of study drug will not be considered a dose limiting toxicity.
- Any Grade 2 non-hematological toxicity that persists for  $\geq 7$  days and is considered sufficiently medically significant or sufficiently intolerable by patients that it requires treatment interruption.
- Any adverse event requiring interruption of study drug for  $>7$  days or which recurs upon drug re-challenge.

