## 9.0 DOSE MODIFICATIONS FOR ADVERSE EVENTS

**The study PIs must be notified of any dosage modification.**

- 1. Dose modifications for hematological toxicity** (Of note, such adverse events have been observed in patients with CML (chronic myelogenous leukemia), likely contributed by concurrent morbidities).
  - If a patient experiences Grade 3 neutropenia (ANC $<1000$ ) or Grade 3 thrombocytopenia (platelets  $<50,000/\text{mm}^3$ ) with or without Grade 1 or 2 non-CNS hemorrhage, the treatment will be withheld. Counts should be checked twice weekly during this time. If the toxicity resolves to meet on study parameters within 14 days of drug discontinuation, the patient may resume treatment with the dose reduced as mentioned in Section 6.1. Treatment should resume 14 days from drug discontinuation even if toxicity has resolved before 14 days in order to allow for a full 2-week rest period before resuming drug.
  - If a patient experiences Grade 1 CNS hemorrhage or Grade 3 or  $>$  non-CNS hemorrhage, the treatment will be withheld. Treatment will not be resumed and the participant will discontinue study drug permanently.
  - If toxicity does not resolve to meet on study parameters within 14 days of drug discontinuation, the patient must be removed from protocol therapy.
  - If dose-limiting toxicity recurs in a patient who has resumed treatment at the reduced dose (maximum of 2 dose reductions allowed), the patient must be removed from protocol therapy.
  - Myeloid growth factors will not be used on study.
- 2. Dose modifications for non-hematological toxicity.**
  - If a patient experiences non-hematologic DLT as defined in Section 8, the treatment will be withheld. If the toxicity resolves to meet on study parameters within 14 days of drug discontinuation, the patient may resume treatment with the dose reduced as mentioned in Section 6.1 (see Appendix A). Treatment should resume 14 days from drug discontinuation even if toxicity has resolved before 14 days. Doses reduced for toxicity will not be re-escalated, even if there is minimal or no toxicity with the reduced dose.
  - If toxicity does not resolve to meet on study parameters within 14 days of drug discontinuation, the patient must be removed from study.
  - If dose-limiting toxicity recurs in a patient who has resumed treatment at the reduced dose level, the patient must be removed from protocol therapy.

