## **13.0 CRITERIA FOR REMOVAL FROM PROTOCOL THERAPY**

1. Adverse Events requiring removal from study
2. Refusal of further protocol therapy by patient/parent/guardian.
3. Non-compliance that in the opinion of the investigator does not allow for ongoing participation, including <70% of drug prescribed being taken. Compliance will not be contingent on completion of the pain journal as this not the primary endpoint of the study.
4. Physician determines continued protocol therapy is not in the patient's best interest.

Patients who are off protocol therapy are to be followed until they meet the criteria for Off Study (see below). Ongoing adverse events, or adverse events that emerge after the patient is removed from protocol therapy, but within 30 days of the last dose of investigational agent, must be followed and reported via RDE and AERS (if applicable). Follow-up data will be required unless consent is withdrawn.

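### Section 6.1 contradicts itself and Section 9 on when a patient may restart imatinib after a toxicity hold: the 14-day clock starts at different events and the recovery thresholds differ.

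*Combined protocol and SAP*

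**What the plan says.** Section 6.1 (Dosage) holds two rules in one paragraph. The resume sentence reads: "If the toxicity resolves to meet study parameters within 14 days of drug discontinuation, the patient may resume treatment with the dose reduced". The stop sentence, two sentences later, reads: "Subjects who fail to recover to a <= grade 2 or baseline within 14 days of AE onset will permanently discontinue study drug".

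Section 9 repeats the resume rule for non-hematologic toxicity: "If the toxicity resolves to meet on study parameters within 14 days of drug discontinuation, the patient may resume treatment with the dose reduced as" set out in Section 6.1. Its hematologic rule has the same threshold and clock. Section 6.1 refers the reader to Sections 8 and 9, and Section 9 refers back to 6.1 for the reduction. Neither says which prevails.

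Section 8 makes some Grade 2 events dose-limiting: "Any Grade 2 non-hematological toxicity that persists for" at least 7 days, if it is significant or intolerable enough to require interruption.

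For unresolved toxicity, Section 9 takes a hematologic case off protocol therapy. For a non-hematologic case it says: "If toxicity does not resolve to meet on study parameters within 14 days of drug discontinuation, the patient must be removed from study". Section 13 keeps the two states apart: "Patients who are off protocol therapy are to be followed until they meet the criteria for Off Study (see below".

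**The concern.** Whether a patient restarts should follow from the event and its course. Here it can depend on which sentence the site reads. The two sentences differ in what counts as recovery and in the day from which 14 days are counted.

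Two sites apply these rules to 20 patients with sickle cell anemia. The decision settles who stays on drug up to the Month 6 paired test in Section 15.4. It also enters the count of adverse events leading to discontinuation, which Section 15.2 names as a main basis of the safety assessment. If the rule is ambiguous, that count partly reflects how each site read the protocol.

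The end state matters as well. A patient off therapy is still followed, whereas a patient off study is not.

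**Working it through.** The plan gives no figure to reproduce. The check sets the rules side by side and finds where they give opposite decisions.

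**Clock.** Inputs:
- Stop sentence (6.1): the deadline is day 14 after onset.
- Resume sentence (6.1) and Section 9: the deadline is day 14 after drug is stopped, and restart takes place on day 14 of the hold.
- h, the days from onset to hold. The documents do not give it, so 0, 1, 3 and 7 are illustrative.
- Assumption: both thresholds are met on the same day R, counted from onset as day 0.

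The stop sentence ends treatment if R > 14. The other rule permits resumption if R − h ≤ 14, that is R ≤ 14 + h. They conflict when 14 < R ≤ 14 + h, which is a window of h days.

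| h | Recovery days in conflict |
|---|---|
| 0 | none |
| 1 | 15 |
| 3 | 15 to 17 |
| 7 | 15 to 21 |

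Example in conflict: h = 3, R = 16. Stop sentence: 16 > 14, permanent discontinuation. Other rule: 16 − 3 = 13 ≤ 14, so resumption is permitted on day 3 + 14 = 17. This does not depend on what *study parameters* means, because both thresholds are taken as met.

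Example in agreement: h = 0, R = 12. Both rules leave the patient eligible to restart, on day 14.

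A delay between onset and hold is plausible. Section 6.0 schedules visits every 30 days ± 7 days and weekly safety contacts only in the first two months. A symptom that starts between later visits may be reported some days after onset.

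**Threshold.** The stop sentence asks for Grade 2 or lower, or baseline. The resume rule asks for *study parameters*. A dose-limiting toxicity that is Grade 2 at onset already satisfies the first, so the stop sentence does not act on it unless it worsens. Whether it satisfies the second cannot be determined from the text. If it has not changed after 14 days of hold, the stop sentence does not end treatment, and the resume sentence neither clearly permits nor clearly bars a restart.

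**End state.** Section 9 has two outcomes for the same failure to resolve: off protocol therapy (hematologic) and off study (non-hematologic). Section 14 lists five off-study criteria: 30 days since the last dose, death, loss to follow-up, withdrawal of consent, and enrollment on another therapeutic study. None is based on toxicity.

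**The case against.** The strongest defense is that the sentences do different jobs: one is a mandatory stop and the other a permission, and a patient must pass both. That answers the threshold difference in part. It does not settle the clock, because the text never says that both tests apply together, and Section 9 states the permission without the onset-based stop.

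The defense also rules out stronger readings that a reader might infer:

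- *Platelets of 60,000 at day 14 mean resume under 6.1 and removal under Section 9.* The count is no longer below Section 9's Grade 3 limit of 50,000, so the stop sentence is not triggered. But 6.1's only permission to restart is the *study parameters* test. If that means the entry limit of 100,000 (an assumption; where Section 8 means entry limits for ALT, it says so), neither section lets this patient resume. Not being stopped is not the same as being allowed to restart.
- *A Grade 2 dose-limiting toxicity has 7 days to recover under 6.1 and 14 under Section 9.* An event already at Grade 2 meets the stop sentence's threshold, so no deadline runs against it there.
- *Removal from study forfeits 30 days of safety follow-up.* After a 14-day hold, about 30 − 14 = 16 days remain. Section 13's first ground for ending protocol therapy itself speaks of removal from study, which suggests loose wording. Section 13 also requires adverse events within 30 days of the last dose to be followed and reported, and Section 7 requires reporting of serious events over the same period.

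Finally, the principal investigators must hear of a dose-limiting toxicity within 24 hours (Section 7) and of every dose modification (Section 9). This limits divergence between sites, but the investigators would still have two rules to choose from.

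**Conclusion.** The contradiction is real, and it lies inside Section 6.1 as well as between 6.1 and 9. Its firm part is the clock: for recovery on days 15 to 14 + h after onset, one rule requires permanent discontinuation and the other permits resumption. This rests on drug being held after onset and on both thresholds being met on the same day. Where drug is held on the day of onset, the clocks agree.

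The threshold difference is a gap, not a second case of opposite decisions. The end-state wording in Section 9 is inconsistent with Sections 13 and 14, but the documents do not support the inference that safety follow-up is lost.

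The number of patients affected cannot be estimated, since the documents give neither the delay to hold nor the time to recovery. Each discordant decision would be 1/20 = 5% of the treated sample. The point should be corrected, but it does not call the design into question.

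**What to change.** Sections 6.1 and 9 must be reconciled so that one recovery threshold and one clock start apply to each type of event. The reconciled text should make clear what *study parameters* means and how events that are Grade 2 from the start are handled. The off-study wording in Section 9's non-hematologic rule must be reconciled with Sections 13 and 14.

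The content is for the sponsor's clinical team. No dose, threshold, clock or stopping rule is proposed here. The cost is a wording amendment, with no added visits or tests.

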## **6.2. Drug Accountability:**

IU Health Investigational Drug Services (IDS) is a division of the Pharmacy Department whose purpose is to assist investigators in procurement, dispensing, and accountability for investigational drugs. All patients treated on this study will have investigational drug coordinated through the IDS.

The Principal Investigator will be ultimately responsible for the investigational product (IP) and the conduct of the study. The PI will delegate functions to IDS that are appropriate.

### **6.2.1 IDS Role and Delegated Functions**

**Protocols:** IDS will maintain a copy of the protocol and investigator's brochure. All protocols that involve IDS must have Institutional Review Board (IRB) approval. IDS should be notified when changes have been submitted to the IRB and have access to the appropriate computer website/program to find the protocol amendments or update.

**IP Inventory:** IDS will provide for adequate inventory including monthly checks, arrange for IP shipments, confirm all shipments as received in good condition and maintain records of all shipments.

**IP Shipments:** IDS will document all IP receipt, dispensing, destruction in accordance with IDS policy and sponsor requirements. To guarantee accurately and timely delivery and immediate shipment confirmation, IP should be shipped directly to IDS:

Investigational Drug Services  
[name]  
[name]  
[name]

**Storage:** IDS will ensure proper storage of all IP in accordance with manufacturer or sponsor recommendations. Storage temperatures will be monitored according to IDS and IU Health monitoring systems.

**Disposal:** Disposal of IP will be in accordance with IDS and IUPUI procedures for Hazardous Waste Disposal. All disposal will be recorded on drug accountability records.

**IP Accountability:** IDS will maintain complete records on of all IP received, dispensed, disposed. Accountability Records will follow standard IDS or NCI Accountability templates unless sponsor required forms are mandated.

**IP Preparation, Labeling and Administration:** IDS staff will write internal standard operating procedures which include:

- Detailed preparation instructions including IV administration and expiration dating
- Proper labeling of prepared IP to comply with Pharmacy Department, Hospital, State or Federal Regulation.
- IDS will design and or approve any prescription or physician orders to be used for the IP to assure all appropriate Pharmacy and Hospital regulations are met.
- 

**Study Conclusion and Record Retention:** At the conclusion of the study, IDS will ensure final disposition of the IP and provide all accountability records, shipping and receipt records, prescriptions and essential study correspondence to the principal investigator for final storage with all study related records.

For more complete details on IDS procedures for various functions please consult the IDS Manual of Operations.

## **7.0 GRADING OF ADVERSE EVENTS**

An adverse event (AE) is defined as any unintended or abnormal clinical observation that is not of benefit to the patient. Either the condition was not present prior to exposure to test medication, or it has worsened in intensity or frequency following exposure to test medication. Adverse events will be graded according to the National Cancer Institute (NCI) Common Terminology Criteria v4.03 (CTCAE):

[http://ctep.cancer.gov/protocolDevelopment/electronic\\_applications/ctc.htm](http://ctep.cancer.gov/protocolDevelopment/electronic_applications/ctc.htm)

Any suspected or confirmed dose-limiting toxicity should be reported immediately (within 24 hours) to the principal investigator.

Principal investigators (PI) must report to the IRB as soon as possible, but in all cases within 5 working days from notification of any event that appears on the **List of Events that Require Prompt Reporting to the IU IRB**.

## **7.1 List of Events that Require Prompt Reporting to the IUPUI IRB.** Any of the following:

- 1.1.1 Event (including adverse events, injuries, side effects during the research study), which in the opinion of the PI
  - 1.1.1.1 caused harm to one or more subjects or others, or placed one or more subjects or others at increased risk of harm; AND
  - 1.1.1.2 was unexpected; AND
  - 1.1.1.3 was related to the research procedures

Note: After the study is closed with the IRB, these events should only be reported if they are profound or they demonstrate long-term risks that would necessitate notifying subjects.

- 1.1.2 Change to the protocol taken without prior IRB review to eliminate apparent immediate hazard to a research subject (e.g. purposeful and for subject safety) (on-site only)
- 1.1.3 Complaint of a subject that indicates unexpected risks, or complaint that cannot be resolved by the research team (on-site only)
- 1.1.4 Interim findings and safety monitoring reports that indicate an unexpected change to the risks or potential benefits of the research, in terms of severity or frequency
- 1.1.5 Publication in the literature that indicates an unexpected change to the risks or potential benefits of the research
- 1.1.6 Change in FDA labeling or withdrawal from marketing of a drug, device, or biologic used in a research study
- 1.1.7 Noncompliance (as defined in this policy and on-site only)

### **Serious Adverse Events (SAE) and unanticipated problems involving risk to subjects or others (UPIRSOs)**

An SAE is defined as any AE occurring at any dose that results in any of the following outcomes:

- death
- a life-threatening adverse experience
- inpatient hospitalization or prolongation of existing hospitalization++
- a persistent or significant disability/incapacity
- a congenital anomaly/birth defect

Other important medical events may also be considered an SAE when, based on appropriate medical judgment, they jeopardize the subject or require intervention to prevent one of the outcomes listed.

++ Note that hospitalizations for the following reasons should not be reported as serious adverse events:

- Routine treatment or monitoring of the studied indication, not associated with any deterioration in condition
- Elective or pre-planned treatment for a pre-existing condition that is unrelated to the indication under study and has not worsened since signing the informed consent
- Social reasons and respite care in the absence of any deterioration in the patient's general condition

- Note that treatment on an emergency outpatient basis that does not result in hospital admission and involves an event not fulfilling any of the definitions of a SAE given above is not a serious adverse event

Any serious or immediately life-threatening adverse experience, including those resulting in death, occurring while the subject is receiving study drug, or within 30 days of the subject's last dose of protocol therapy, regardless of the treating physician's opinion regarding drug relationship, will be reported by telephone and/or e-mail (within 24 hours of the event) to the Study PI and appropriate parties.

**Serious adverse events are to be reported via Oncore on the SAE Form within 5 business days of event notification.**

**Study principal investigators are to be notified of serious adverse events via email within 5 business days of event notification.**

#### **Instructions for rapid notification of unexpected serious adverse events reporting procedures**

When an unexpected serious adverse event occurs, the investigator (study chair) must complete the FDA MedWatch 3500a form in English and assess the relationship to study treatment.

Follow-up information should describe whether the event has resolved or continues, if and how it was treated, and whether the patient continued or discontinued study participation. The MedWatch form and fax confirmation sheet must be retained. Pregnancy follow-up should describe the outcome of the pregnancy, including any voluntary or spontaneous termination, details of the birth, and the presence or absence of any congenital abnormalities or birth defects.

#### **8.0 DEFINITION OF DOSE-LIMITING TOXICITY (DLT)**

DLT will be defined as any of the following events that are possibly, probably, or definitely attributable to imatinib.

##### **1. Non-hematologic dose-limiting toxicity**

- Any Grade 4 non-hematologic toxicity
- Any Grade 3 non-hematologic toxicity with the specific exception of:
  - Grade 3 ALT that return to levels that meet initial eligibility criteria within 7 days of study drug interruption and that do not recur upon rechallenge with study drug. Note: For the purposes of this trial the ULN for ALT is defined as 45 U/L.
  - Grade 3 AST
  - Grade 3 fever or infection <5 days duration
  - Grade 3 hypophosphatemia, hypokalemia, hypocalcemia or hypomagnesemia responsive to oral supplementation within 14 days of initiating supplementation
  - Asymptomatic Grade 3 elevations in amylase or lipase resolving to <Grade 1 within 7 days of study drug interruption and that do not recur upon re-challenge with study drug
- Grade 2 or greater left ventricular systolic dysfunction OR an absolute decrease in shortening fraction of 8 percentage points from baseline.
- Grade 2 allergic reactions that necessitate discontinuation of study drug will not be considered a dose limiting toxicity.
- Any Grade 2 non-hematological toxicity that persists for  $\geq 7$  days and is considered sufficiently medically significant or sufficiently intolerable by patients that it requires treatment interruption.
- Any adverse event requiring interruption of study drug for  $>7$  days or which recurs upon drug re-challenge.

